11.3 Statistical Methods

For the study hypothesis to examine the preliminary effect of a single-session tDCS on depression on negative attention bias, we will use the calculated latency response times pre-tDCS and post-tDCS using the DP and VS tasks and compare change using a paired sample's t-test for each measure. Further, to compare across the groups, we will use ANOVA for before and after effect of tDCS on negative attention bias across the three groups.

As secondary and exploratory, we will also test change in pre- to post- ratings of depressive symptoms and affect. These findings will be collected to inform the power analyses for a larger controlled trial.

12 Source Documents and Access to Source Data/Documents

Source data is all information, original records of clinical findings, observations, or other activities in a study necessary for the reconstruction and evaluation of the study. Source data are contained in source documents. Examples of these original documents, and data records include: hospital records, clinical and office charts, laboratory notes, memoranda, evaluation checklists, pharmacy dispensing records, recorded data from

CONFIDENTIAL

automated instruments, copies or transcriptions certified after verification as being accurate and complete, subject files.

The study case report form (CRF) is the primary data collection instrument for the study. All data requested on the CRF must be recorded. All missing data must be explained. If a space on the CRF is left blank because the procedure was not done or the question was not asked, write "N/D". If the item is not applicable to the individual case, write "N/A". All entries should be printed legibly in blue or black ink. If any entry error has been made, to correct such an error, draw a single straight line through the incorrect entry and enter the correct data above it. All such changes must be initialed and dated. DO NOT ERASE OR WHITE OUT ERRORS. For clarification of illegible or uncertain entries, print the clarification above the item, then initial and date it.

Access to study records will be limited to IRB-approved members of the study team. The investigator will permit study-related monitoring, audits, and inspections by the IRB, government regulatory bodies, and University compliance and quality assurance groups of all study related documents (e.g. source documents, regulatory documents, data collection instruments, study data etc.). The investigator will ensure the capability for inspections of applicable study-related facilities.

Participation as an investigator in this study implies acceptance of potential inspection by government regulatory authorities and applicable University compliance and quality assurance offices.

13 Ethics/Protection of Human Subjects

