4.1 Description of Study Design

In this prospective pilot study we will recruit 25 female participants, ages 18-45 (inclusive), with mild to moderate depression (based on BDI-II score range 14-19 for mild and 20-28 for moderate) as well as 50 healthy control (defined by a BDI > 14) females of the same age range (18-45) to determine if a single-session of tDCS can alter negative attention bias. With the healthy control group, the recruited participants will be assigned to either

CONFIDENTIAL

the easy (n = 25) or difficult/unsolvable (n = 25) pre-tDCS word puzzle task condition. The group assignment will be pseudo-randomized (counterbalanced; e.g., alternating easy and difficult anagram conditions). The primary objective is to study if single-session tDCS will affect attention bias in depression and is not meant to treat depression. Subjects may or may not be receiving treatment for mild-moderate depression. If potential participant is severely depressed during the screening, standard clinical procedures will be used such as advising them to contact their treating physician and/or providing them a crisis hotline number (SAMHSA's National Helpline: [name], or to NYU Langone Psychiatry Associates at [contact].

For this initial pilot study, we are measuring subtle changes in response time latency at the millisecond level for attention bias. Because demographic factors of both age and sex are known to influence response times on attention tasks (Dykiert, Der, & Deary, 2012; Joormann & Gotlieb, 2007), we will limit the contribution of these factors in this initial pilot study.

The study will consist of a single 2.5 hour research visit that will take place at the NYU Ambulatory Care Center ([name]). After written informed consent is obtained (outlined in section 13.1), participants will have an eligibility screening which will include a semi structured interview (MINI). Eligible participants will complete depression and mood self-report questionnaires, two attention bias tasks (dot-probe and visual), and a single 30-minute tDCS session. Total study duration (including analysis, etc.) will be 1 year.

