4.2 Primary Endpoints

We will examine if a single-session tDCS will reduce depression-related negative attention bias before and after the stimulation using the attention bias scores generated using reaction-time based data during the dot probe and visual search task. We will also compare this difference across conditions.

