6.2 Screening/Study Visit

- Obtain written informed consent (*25 minutes or however much time is needed*).
- Conduct eligibility screening/MINI/BDI-II (*15 minutes*)
- tDCS tolerability test (*2 minutes*)
- Administer depression surveys (BAI, HAM-D, and SMDDS) (*15 minutes*)
- Administer computerized attention bias dot-probe and visual search task (*30 minutes*)
- Administer pre-tDCS measures (PANAS and AMS; *10 minutes*)
- Complete tDCS session (*30 minutes*)
- Repeat PANAS and AMS (*10 minutes*)
- Repeat attention bias dot-probe task and visual search (*30 minutes*)

7 Study Procedures/Evaluations

After participants provide written informed consent, the following study procedures will take place during a single 2.5 hour research visit:

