7.4.1 Dot Probe Task

The dot probe task is an established procedure for measuring and manipulating biases in attention associated with depression in adults and children (MacLeod, Mathews, & Tata, 1986; Eldar et al., 2008, Joormann &

CONFIDENTIAL

Gotlieb, 2007; Pekham et al., 2010). The dot-probe task will be used to assess depression-related attention bias before and after tDCS administration.

To complete the Dot-Probe task, participants will be shown two emotional images (e.g., sad and neutral pair or happy and neutral pair) simultaneously followed by a target in the location of one of the emotional images. Response latencies to targets replacing either the negative/positive or neutral images will be measured before and after training which will be the primary study outcome. Emotional stimuli used are a selection of negative, positive, and neutral pictures taken from a standardized and often used set of emotional faces called the racially diverse affective expression [RADIATE; Conley et al., 2018].

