7.4.2 Visual Search Task

In addition, the Visual Search task (e.g., Wolf & Horowitz, 2017) will be administered to further assess attention bias, particularly examining the interference and facilitation effects in attention using emotional stimuli (Rinck & Becker, 2005). The task uses emotional faces or words as stimuli, where the participant is instructed to search for the face that does not fit into the search set with respect to gender (i.e., the only male under three female faces, or the only female under three male faces), where the target and distractors are expressing different or same emotions (i.e., neutral-neutral, sad-neutral, happy-neutral, neutral-sad, neutral-happy, sad-sad, and happy-happy). Studies have shown that individuals with emotional and stress-related disorders show interference effect (i.e., emotional stimuli being the distractor) and facilitation effect (i.e., emotional stimulus being the search target), but less is known about depression (Bodenschatz et al., 2021; Rinck & Becker, 2005; Pineles et al., 2009). This study will use this task as an outcome measure of AB alongside the DP task. For this task, mean response time (the time between display onset and button press) to the target stimulus for each stimulus type is measured as the main outcome variable.

7.5 tDCS Session

tDCS Dose Selection and Tolerability: Participants will undergo a tolerability test to ensure tolerance of the stimulation intensity. In under 2 minutes, the tDCS device ramps up to the target stimulation of 2.0mA and ramps back down to 0mA. The tolerability test can be aborted at any time if the participant is uncomfortable. If 2.0mA stimulation is not tolerated, the participant will be given the option to proceed with a second tolerability test at a lower stimulation amperage (1.5 mA). Participants who cannot tolerate 1.5mA will be excluded as a screen failure.

tDCS settings: The MINDD STIM tDCS system is composed of a management component, treatment module, single-use sponge patches and supporting patches, a headband to hold in position the sponge patches, and 2 cables. A trained study technician will program the stimulation device through the management component setting to the following stimulation parameters:

- **Stimulation intensity:** 2.0 mA or 1.5 mA
- **Stimulation duration:** 30 minutes
- **Ramp up duration:** 30 seconds (beginning of stimulation)
- **Ramp down duration:** 30 seconds (end of stimulation)

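### The primary variable is a bias score in 4.2 but a latency in 7.4.1, 7.4.2 and the paired t-test of 11.3, and no score is defined

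*Combined protocol and SAP*

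**What the plan says.** Four places in the protocol name the variable to be analysed.

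- **4.2 Primary Endpoints** sets out to show reduced negative bias "using the attention bias scores generated using reaction-time based data during the dot probe and visual search task".
- **7.4.1 Dot Probe Task** describes image pairs ("sad and neutral pair or happy and neutral pair", given as examples). It says that latencies to targets replacing the negative/positive "or neutral images will be measured before and after training which will be the primary study outcome". No training is described anywhere in the protocol; the intervention is the tDCS session.
- **7.4.2 Visual Search Task** says that mean response time "to the target stimulus for each stimulus type is measured as the main outcome variable". It lists seven target and distractor combinations: "neutral-neutral, sad-neutral, happy-neutral, neutral-sad, neutral-happy, sad-sad, and happy-happy". Facilitation (emotional target) and interference (emotional distractor) are explained in words, but no contrast between named combinations is stated.
- **11.3 Statistical Methods** states the aim as the effect on negative attention bias. It then says "we will use the calculated latency response times pre-tDCS and post-tDCS using the DP and VS tasks and compare change" by paired t-test for each measure, and applies an ANOVA across the three groups to negative attention bias.

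On timing, 6.2 has both tasks done before stimulation and again afterwards in the same visit ("Repeat attention bias dot-probe task and visual search"). On purpose, 11.2 says the results will give a preliminary evaluation of effect and feed power analyses for a later trial.

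**The concern.** A response latency and an attention bias score answer different questions. A latency says how fast the participant responds. A bias score says how much faster or slower she responds when the stimulus is sad rather than neutral. Participants who repeat a reaction-time task in the same visit may get faster with practice or slower with fatigue. A paired test on latency picks up either one and could report it as a tDCS effect on bias.

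If a score is used instead, its definition is still open. The dot probe subtraction is not written down, and the seven visual search combinations allow several contrasts. The choice could therefore be made after the data are seen, and the reference in 11.3 to each measure has no fixed meaning. In both cases the harm falls on what the pilot is for: an effect size for raw latency is not an effect size for bias, and would be the wrong input to a power calculation for a trial of bias.

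**Working it through.** **The plan's own figures.** The only sample-size figures are 25 enrolled and 20 evaluable per group (5.5, 11.2): 3 × 25 = 75 and 3 × 20 = 60, as stated. The plan gives no alpha, power, effect size, SD or expected retest change, so there is no power figure to reproduce. Everything below that needs such values is assumed.

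**Time between runs (6.2).** tDCS takes 30 min and the repeat PANAS and AMS 10 min, which gives 40 min. If the first PANAS and AMS (10 min) come after the first run of the tasks, as 6.2 lists them, the gap is 50 min.

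**What a common shift does.** Let s be a change in speed that is the same for all trial types between the two runs, with no tDCS effect on bias.

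- Latency for one trial type: mean of (post − pre) = s. The shift is the whole of the expected difference.
- Score B = RT(neutral) − RT(sad): change = [RT(neutral) + s − RT(sad) − s] − [RT(neutral) − RT(sad)] = 0. The shift cancels.
- Three-group comparison of latency change: if every group shifts by s, the group means differ by s − s = 0. An equal shift cancels here even for latencies.

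**Size for the paired latency test.** With d = s / (SD of the latency change), the t statistic is noncentral with n − 1 degrees of freedom and noncentrality d√n. Alpha is assumed two-sided 5%; critical t = 2.093 at n=20 and 2.064 at n=25.

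| d | n=20: d√n | n=20: significant | n=25: d√n | n=25: significant |
|---|---|---|---|---|
| 0.2 | 0.894 | 13.6% | 1.000 | 16.1% |
| 0.4 | 1.789 | 39.7% | 2.000 | 48.4% |
| 0.6 | 2.683 | 72.1% | 3.000 | 82.1% |

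In milliseconds the range is too wide to locate this trial. At n=20 an assumed gain of 10 ms with SD of change 70 ms gives 9%, 20 ms with SD 50 ms gives 40%, and 40 ms with SD 30 ms gives about 100%.

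**The score under the same conditions.** In simulation (40,000 runs, n=20 and n=25, general speed-up of 0 to 40 ms, no effect on bias), the paired test on the difference score was significant about 5% of the time. This held whether the speed-up was a constant or a proportion of the latency. In the proportional case a small remainder is left: with the assumed 15 ms bias and 550 ms latency, a 40 ms speed-up changes the score by 15 × 40/550 = 1.1 ms.

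**The case against.** The strongest reply is that the sections describe one plan at two levels: 7.4.1 and 7.4.2 say what is recorded, and 4.2 says what is derived from it. Several points support this. Section 11.3 opens with negative attention bias and calls the latencies calculated. Section 7.4.1 names the two probe positions that would be subtracted. Section 4.1 says "we are measuring subtle changes in response time latency at the millisecond level for attention bias", which treats latency as the means of measuring bias. This stands as evidence of intent, and a bias score is the likelier reading. It does not settle the matter, because 7.4.1 and 7.4.2 give the latencies the status of primary or main outcome and no section supplies the subtraction.

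Three stronger readings are tempting, and the documents support none of them.

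- **That the trial will test raw speed, with a false-positive rate of 40% or 72%.** The text permits a latency analysis but does not commit to one, and every shift size above is assumed.
- **That many separate tests would be falsely significant.** If the two example pair types are the full set, there are 2 × 2 = 4 dot probe cells and 7 visual search cells, 11 in all. Only 5 involve sad stimuli (2 dot probe, 3 visual search), so at a 0.4 SD shift about 5 × 0.397 = 2.0 tests that could be taken as negative bias would be expected to be significant. A uniform speed-up would also show in the happy and neutral-neutral cells, where a careful reader would notice it. The fair comparison is per test.
- **That the group comparison fails too.** An equal shift cancels there, and 11.1 includes the control groups partly to show expected ranges of change in the tasks.

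The exploratory label lowers the stakes but does not remove the point, since the estimates are meant to be carried forward.

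**Conclusion.** The point holds as a conflict in the text with a conditional consequence. The mismatch between 4.2, 7.4.1, 7.4.2 and 11.3, and the absence of any score definition, are certain from the documents. That a general shift would enter a paired latency test, and cancel in a within-session difference, follows by algebra. How large the shift would be here is unknown. The figures of 14%, 40% and 72% against about 5% illustrate common shifts of 0.2, 0.4 and 0.6 SD at n=20, with two-sided 5% and no tDCS effect assumed.

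It should be put right before analysis. It does not put the data at risk, because latencies by stimulus type are recorded and scores can be computed from them. The lack of a described sham group limits attribution to tDCS whichever variable is used; that is a separate matter.

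**What to change.** In 7.4.1, 7.4.2 and 11.3, replace latencies as the analysed variable with bias scores that are within-session differences between trial types. Fix them before analysis, and use the same scores in the paired t-test and the ANOVA. Section 4.2 can then refer to these definitions.

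- **Dot probe:** mean RT with the probe at the neutral face minus mean RT with the probe at the sad face, in sad-neutral pairs.
- **Visual search:** name the facilitation and interference contrasts. For example, facilitation = neutral-neutral minus sad target among neutral distractors; interference = neutral target among sad distractors minus neutral-neutral. The investigators may prefer other contrasts, including ones that use the happy trials, provided they are named in advance.
- **11.3:** state that each measure means these scores.
- **7.4.1:** replace the reference to training with the tDCS session.

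The cost is wording only; the example contrasts use trial types already in the tasks, so no added participants, visits or assessments are needed. There is a statistical price. Difference scores are noisier than raw latencies, and they do not remove habituation specific to bias, regression to the mean, or the limit set by having no described sham group. For scale, a residual bias-specific shift of 5 ms with SD of change 60 ms would still be significant 6% of the time at n=20, and 10 ms with SD 30 ms 29% of the time (all four values assumed).

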Statistical Analysis	Pre-post tDCS comparison analyses using t-tests and correlations

CONFIDENTIAL

Schematic of Study Design

Pre-Screen	
• Eligibility pre-screen to determine general eligibility including BDI-II screen
Study Visit	
• Obtain Informed Consent• Mini International Neuropsychiatric Interview (MINI) (Screening)• Beck Depression Inventory (BDI-II) (Screening)• Beck Anxiety Inventory (BAI)• Hamilton Depression Rating Scale (HAM-D)• Symptoms of Major Depressive Disorder Scale (SMDDDS)• Healthy controls will complete a brief computer-based word puzzle task before the tDCS session, assigned to one of two conditions: difficult/unsolvable or easier
Pre-tDCS Administration	
• Positive and Negative Affect Schedule-SF (PANAS);• Analog Mood Scale (AMS)• Dot Probe Task (DP) and Visual Search (VS) Task
tDCS Administration	
• tDCS tolerability test• 30 minutes of tDCS (up to 2.0mA)
Post-tDCS Administration	
• PANAS• AMS• DP and VS Tasks

CONFIDENTIAL

Key Roles

Principal Investigator:

[name]
NYU Langone Health
Department of Neurology
[name]
[contact]
[contact]

Sub-Investigators:

[name]
NYU Langone Health
Department of Neurology
[name]
[contact]
[contact]

[name]
Department of Neurology, NYU Langone Health
[name]
[name]
[contact]
[contact]

1 Introduction, Background Information and Scientific Rationale

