11.2 Sample Size Determination

The primary objective of this study is to test change in negative attention bias in people with mild to moderate depression following a single session of DLPFC tDCS, and see if their outcomes differ from that of healthy controls.

This is a pilot study to assess the feasibility of a single-session tDCS in a small sample, and the findings will provide preliminary evaluation of effect and inform power analyses for use in a clinical trial design.

A total of $N = 75$ ($n=25$ participants for each group) will be enrolled to obtain evaluable target of $N=60$ ($n = 20$ for each group) based on the estimated number of eligible participant for each group contacts across the study period.

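### The primary outcome is described inconsistently, and each latency measure is tested with no ranking or success rule; one defined dot-probe negative-bias score should be named as primary

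*Combined protocol and SAP*

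**What the plan says.** The combined protocol and SAP describes the main outcome in several places.

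- **Section 4.2 (Primary Endpoints):** change in negative attention bias, "using the attention bias scores generated using reaction-time based data during the dot probe and visual search task". Both tasks count, and the quantity is a score.
- **Section 7.4.1 (Dot Probe Task):** response latencies to targets replacing the emotional or neutral image "will be measured before and after training which will be the primary study outcome". One task counts, and the quantity is a latency.
- **Section 7.4.2 (Visual Search Task):** for that task, mean response time "to the target stimulus for each stimulus type is measured as the main outcome variable". Seven target-distractor combinations are listed.
- **Synopsis, Endpoint row:** attention bias and mood together, unranked. Section 4.3 makes mood and affect secondary.

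Section 11.3 takes the calculated latencies from both tasks before and after stimulation and will "compare change using a paired sample's t-test for each measure", followed by an ANOVA across the three groups. The synopsis describes the analysis only as "Pre-post tDCS comparison analyses using t-tests and correlations". No significance level, sidedness, bias-score formula, ranking of measures or criterion for success appears anywhere.

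Section 11.1 states a directional hypothesis, that stimulation will reduce negative attention bias in the depressed group, and also calls the work exploratory. Section 11.2 says the findings will "inform power analyses for use in a clinical trial design".

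**The concern.** Two analysts could follow this plan faithfully and test different quantities. One could compare bias scores from both tasks, as in section 4.2. The other could compare raw latencies, as in sections 7.4.1 and 11.3. These are not interchangeable: a bias score is a contrast between conditions, whereas a single latency also reflects general speed.

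Because nothing is ranked and no success rule is given, a significant change on any one measure could be reported as support for the hypothesis in section 11.1, and the choice could be made after the data are seen. There is a second cost, which matters even in a pilot. The results are meant to feed the power calculation for a larger trial, and an effect size taken from whichever measure moved most will tend to be too large.

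**Working it through.** **Is there a figure in the plan to reproduce?** No. Alpha, power, effect size and standard deviation are not stated. The only design figures are 25 enrolled and 20 evaluable per group (sections 5.5 and 11.2).

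**Latency against score.** Let S be the mean latency to probes replacing the sad face, N the mean latency to probes replacing the neutral face, and bias = N − S. Section 7.6 repeats the task within the same visit. If every response becomes faster by an amount d, both latencies fall by d, but the bias change is (N − d) − (S − d) − (N − S) = 0. A paired t-test on either latency would then tend towards significance with no change in bias.

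**How many measures?**
- Low count: one negative-bias score per task, so k = 2 (a reading of section 4.2).
- High count: every latency cell. Visual search has 7 types (section 7.4.2). The dot probe has 4 cells if both sad-neutral and happy-neutral pairs are used, with the probe at the emotional or the neutral face. Section 7.4.1 gives these pairs only as examples, so the 4 is inferred. Total k = 4 + 7 = 11.

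**Chance of at least one false positive in either direction**, assuming two-sided 5% per test and no true change, with independent measures:
- k = 2: 1 − 0.95² = 9.75%
- k = 11: 1 − 0.95¹¹ = 43.1%

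Latencies from one person in one visit are likely to be positively correlated. Simulated paired t-tests (n = 20, 40,000 runs, equal correlation between changes) give:

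| Correlation | k = 2 | k = 11 |
|---|---|---|
| 0.3 | 9.5% | 37.6% |
| 0.5 | 8.9% | 31.2% |
| 0.7 | 8.1% | 22.9% |
| 0.9 | 7.0% | 13.8% |

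**Counting only the hypothesised direction.** Each two-sided 5% test has a 2.5% chance of a false positive in the favourable direction:
- k = 2: 1 − 0.975² = 4.9%
- k = 11: 1 − 0.975¹¹ = 24.3% under independence, and by simulation about 19% to 20% at correlation 0.3 and 16% at 0.5

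The 11-measure figure supposes that each raw latency has one direction that counts as favourable. The plan does not define one.

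**Effect of choosing the best-looking measure.** With no true effect, n = 20 and the largest favourable change selected, the expected standardised change is:
- about 0.35 SD for 11 independent measures (expected maximum of 11 standard normals, about 1.59, divided by √20)
- about 0.25 SD at correlation 0.5 (0.35 × √0.5)
- about 0.13 SD for two independent measures

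**The case against.** The strongest reply is that this is a declared exploratory pilot. Section 11.1 says so, sections 11.2 and 11.3 speak of preliminary effects, and no decision hangs on a p-value. That stands as far as it goes: formal alpha adjustment would be out of place. It does not explain why the main outcome differs between sections.

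It can also be said that the conflict is smaller than it looks. Section 7.4.2 speaks only for its own task and uses visual search alongside the dot probe, which agrees with section 4.2, so it is not a rival trial-level primary. Bias scores are built from latencies, so part of the gap is missing detail. Both remarks are fair. What remains is that section 7.4.1 singles out the dot probe, section 4.2 does not, and section 11.3 applies its t-tests to latencies.

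A reader might infer something stronger: that there are 11 co-primary measures, each tested at 5%, so a chance finding is likely. The documents do not support that.
- No alpha is stated.
- The term co-primary is not used. If it meant that all measures must succeed, there would be no inflation.
- The count of 11 is an upper reading that rests partly on an example. Four of the seven visual-search types contain no sad face and cannot by themselves show a reduction in negative bias.
- A chance of 43% is below one half. Even under independence, 14 tests would be needed to pass 50% (1 − 0.95¹⁴ = 51.2%).

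Nor do the documents show that the measure will be picked after the data are seen. They only leave that open.

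**Conclusion.** The point holds as an inconsistency in the primary outcome, combined with an analysis section that does not resolve it. Sections 4.2 and 7.4.1 name different primary quantities, the synopsis leaves mood unranked against section 4.3, and section 11.3 tests latencies measure by measure without a score formula, ranking or success rule.

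The false-positive risk is moderate and depends on the reading. At an assumed two-sided 5% it runs from 9.75% for two independent measures to a ceiling of 43% for 11, with positive correlation lowering both. Restricted to the hypothesised direction, it is about 5% to 24% under independence. These figures also assume no general speeding up on repetition, which would make raw-latency tests significant more often without any change in bias.

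The matter should be corrected, but it does not undermine the pilot.

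**What to change.** - **Sections 4.2, 7.4.1 and 11.3:** name one primary measure, the pre-to-post change in the dot-probe sad-versus-neutral bias score in the depressed group. This fits the dot-probe emphasis of 7.4.1, the scores of 4.2 and the negative-bias hypothesis of 11.1.
- **Section 11.3:** give the formula, for example mean latency to probes replacing the neutral face minus mean latency to probes replacing the sad face. Use the change in this same score in the three-group ANOVA.
- **Secondary measures:** report the dot-probe happy-bias score and the visual-search interference and facilitation scores as estimates with 95% confidence intervals. State that they will not be used to claim that the hypothesis is met.
- **Synopsis and section 7.4.2:** align the wording, with mood shown as secondary.

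No formal alpha adjustment is needed. The cost is protocol wording only, with no extra participants, visits or assessments. The one real concession is that visual search loses the primary status that section 4.2 now gives it.

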11.1 Study Hypotheses

A single-session tDCS to the left DLPFC will reduce negative attention bias in people with mild to moderate depression. There will be cohort differences across mildly depressed vs. healthy controls with easy anagram vs. healthy controls with difficult anagram (situational stressor) where the reduction of negative attention bias would be greatest in the depressed group compared to the healthy controls.

The primary objective of this study is exploratory data collection. These pilot study findings will be the necessary first step to inform future study design and hypotheses. We are collecting the healthy control pilot data to better interpret the pilot findings in patients with depression, and to provide us with expected ranges of change in our task measures. This inclusion of the anagram task is exploratory to inform future study designs. The use of the challenging anagram task is based from literature where the same paradigm has been used in healthy controls to study temporary states of negative affect (e.g., frustration, anxiety; Myruski et al., 2021).

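### The three-group omnibus ANOVA in section 11.3 has no direction, so it does not test the section 11.1 hypothesis that bias falls most in the depressed group

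*Combined protocol and SAP*

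**What the plan says.** Section 11.1 gives two hypotheses. The first is that stimulation reduces negative attention bias in depressed participants. The second compares three cohorts (depressed, healthy with easy anagrams, healthy with difficult anagrams) and predicts that "the reduction of negative attention bias would be greatest in the depressed group compared to the healthy controls".

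Section 11.3 gives two analyses. Within a group, the plan will "compare change using a paired sample's t-test for each measure". Between groups, "we will use ANOVA for before and after effect of tDCS on negative attention bias across the three groups". No contrast, pairwise or post-hoc comparison, direction, alpha or covariate follows. The protocol summary lists only t-tests and correlations.

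Section 4.2 sets the outcome as before-and-after change, "using the attention bias scores generated using reaction-time based data during the dot probe and visual search task". Section 11.2 enrols 25 per group to obtain 20 evaluable. That number is "based on the estimated number of eligible participant for each group contacts across the study period", not the result of a power calculation.

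**The concern.** The second hypothesis has a direction and singles out one group. An omnibus F test asks only whether the three mean changes are all equal. It can be significant because the two control groups differ from each other while the depressed group is no different from the easy-anagram controls.

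That possibility is built into the design. The Rationale section describes the difficult condition as a situational stressor, and section 11.1 ties the task to temporary negative affect.

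With no follow-up comparison named, any statement that the depressed group improved most would rest on choices made after seeing the data. Section 11.3 also wants the results to inform the power analysis of a larger trial. A 2-df F supplies no signed difference for that purpose.

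**Working it through.** **Inputs from the documents.** Three equal groups, 20 evaluable each (11.2). The plan's own arithmetic reproduces: 20 of 25 evaluable implies a 20% loss, 20 / 0.80 = 25, and 3 × 25 = 75. No power, alpha, effect size or SD is stated, so there is no power figure to reproduce.

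**Assumptions.** Two-sided alpha 0.05; SD of change equal to 1 in every group; d is the difference in mean reduction in SD units. Error df = 3 × 19 = 57. Figures apply to each task measure separately. With two time points, the group-by-time test and a one-way ANOVA on change are the same 2-df test.

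Mean reductions are written (depressed, easy, difficult).

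**1. Omnibus F(2, 57).** Noncentrality λ = 20 × Σ(mean − grand mean)².
- Only depressed differs, (0.8, 0, 0): λ = 20 × 0.64 × 2/3 = 8.53, power 72%.
- Only difficult-anagram controls differ, (0, 0, 0.8): the sum of squares is the same, so λ = 8.53 and the rejection rate is 72%.
- At d = 0.5 for depressed only: λ = 20 × 0.25 × 2/3 = 3.33, power 34%.

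The test therefore rejects equally often when the hypothesis is true and when it is false in this way.

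**2. Depressed minus the average of the controls (t, 57 df).** The standard error is √(1.5/20) = 0.274.
- Controls alike, d = 0.8: 0.8 / 0.274 = 2.92, power 82% against 72% for the omnibus.
- Graded pattern (depressed 0.8, one control group 0.4, the other 0): contrast 0.8 − 0.2 = 0.6, and 0.6 / 0.274 = 2.19, power 58%. The omnibus has λ = 20 × (0.16 + 0 + 0.16) = 6.4, power 59%.
- Depressed equal to easy controls and stressed controls improving 0.8 SD less, (0, 0, −0.8): contrast 0.4, and 0.4 / 0.274 = 1.46. It rejects in the hypothesised direction 30% of the time, although the depressed group is not the greatest.

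**3. Depressed must exceed each control group.** Each pairwise standard error is √(2/20) = 0.316. The two comparisons share the depressed mean, so their estimates correlate 0.5. Both two-sided 5% tests must be significant in the hypothesised direction. With the control groups alike:
- d = 0.8: 0.8 / 0.316 = 2.53 for each, joint power about 56%.
- d = 0.5: 0.5 / 0.316 = 1.58 for each, joint power about 19%.

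If the depressed group equals either control group, a false claim needs that comparison to fall in its upper 2.5% tail. The chance is at most 2.5%, whatever the other control group does.

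**The case against.** The strongest reply is that little hangs on this test. Section 11.1 calls the main purpose exploratory data collection, with controls included to show expected ranges of change. The first-listed analysis is the within-group paired t-test, which this point does not touch, and nothing stops the team from reporting group means after an ANOVA. This stands as a limit on severity. It does not remove the mismatch: the plan states a directional between-group hypothesis and names no analysis that addresses it.

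Three stronger readings are tempting, and the documents do not support them.

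- A reader might infer that the omnibus test always wastes power. The gain from a single averaged contrast depends on the two control groups responding alike; under the graded pattern it vanishes. There is also no planned power to set a loss against.
- A reader might infer that comparing the depressed group with the average of the controls settles the matter. It does not test whether the reduction is greatest in the depressed group, and it misleads 30% of the time in the case shown.
- A reader might infer that the plan ignores age, since section 4.1 says that "demographic factors of both age and sex are known to influence response times on attention tasks". The same paragraph says the pilot will limit these influences, and entry is restricted to women aged 18–45 in all groups. The analysed quantity is within-person change, so an additive effect of age on speed cancels. The depressed group is not randomised against controls, so some age imbalance within that range is possible, but the documents give no relation between age and change.

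**Conclusion.** The point holds for the between-group hypothesis. The only between-group test named cannot show direction, and it rejects 72% of the time at 20 per group whether the depressed group or only the stressed controls differ by 0.8 SD. This rests on alpha 0.05, equal SDs of change and 20 evaluable per group; the first two are assumptions.

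It is a mismatch between hypothesis and test in an exploratory pilot. It is not a general loss of power, and it is not a failure to deal with age.

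**What to change.** In section 11.3, make the test of the second hypothesis two pre-specified differences in change in bias score: depressed versus easy-anagram controls and depressed versus difficult-anagram controls. Give each a 95% CI using the pooled three-group error, and state alpha and sidedness. Claim that the reduction is greatest in the depressed group only if it exceeds both control groups. Because both are required, that claim needs no multiplicity adjustment for the pair. Keep the omnibus F as descriptive.

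The contrast with the average of the controls may be reported as a supplement, with the caution that it is interpretable only if the two control groups respond alike. Age adjustment is at most an optional sensitivity analysis.

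The change needs no new data, visits or participants. Its price is lower power for the joint claim than for the omnibus test (56% against 72% at 0.8 SD, 19% against 34% at 0.5 SD, controls alike). In a pilot that states no power, the two estimates and their intervals are the more useful product: each interval is about ± 2.00 × 0.316 = 0.63 SD.
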